## 7.4 Follow-Up for Drug Discontinuation/Participant Withdrawal from Study

If a participant discontinues study treatment and is withdrawn from the study for any reason, the study site must immediately notify the medical monitor. The date and the reason for study discontinuation must be recorded on the electronic case report form (eCRF). Participants who withdraw prematurely are to attend an Early Termination Visit, if possible, and complete all assessments.

In the event that a participant discontinues prematurely from the study due to a treatment-emergent adverse events (TEAE) or serious TEAE, the TEAE or serious TEAE will be followed until it resolves (returns to normal or baseline values) or stabilizes, or until it is judged by the Investigator to be no longer clinically significant.

Once a participant is withdrawn from the study, the participant may not re-enter the study.

#### 8 TREATMENTS

Participants will be screened for enrollment. If they meet all inclusion criteria and do not meet exclusion criteria, they will be referred for pre-treatment biopsy of either an unresectable lesion or a metastatic lesion. After biopsy, each participant will be randomized either to Arm A (combination ipilimumab and nivolumab) or Arm B (ipilimumab alone).

#### Arm A:

- Participants will be required to start treatment within 14 days of their pre-treatment biopsy. The pre-treatment biopsy is considered standard of care.
- One dose of ipilimumab and nivolumab administered together constitutes one cycle; they will be administered in the manner described in Section 8.4.
- Cycles will be administered every 21 days±4 days for up to 4 cycles.

- CT scans will be administered at weeks 12 and 18 and every 12 weeks for up to 2 years after study treatment begins. These are considered standard of care.
- Blood will be drawn at every cycle during treatment and during follow-up visits. Standard bloodwork, such as complete blood count (CBC) and comprehensive metabolic panel (CMP), are part of routine care. Other bloodwork (approximately 40 mL) will be drawn which is solely for the purpose of research.
- An on-treatment biopsy will be required within 14 days ± 5 days of the start of Cycle 1. This is solely for the purpose of research. All reasonable efforts will be made to biopsy the same lesion pre- and on-treatment.

#### Arm B:

- Participants will be required to start treatment within 14 days of their pre-treatment biopsy. The pre-treatment biopsy is considered standard of care.
- One dose of ipilimumab constitutes one cycle; it will be administered in the manner described in Section 8.4.
- Cycles will be administered every 21±4 days for up to 4 cycles.
- CT scans will be administered at weeks 12 and 18 and every 12 weeks for up to 2 years after study treatment begins. These are considered standard of care.
- Blood will be drawn at every cycle during treatment and during follow-up visits. Standard bloodwork, such as CBC and CMP, are part of routine care. Other bloodwork (approximately 40 mL) will be drawn which is solely for the purpose of research.
- An on-treatment biopsy will be required within 14 days ± 5 days of the start of Cycle 1. This is solely for the purpose of research. All reasonable efforts will be made to biopsy the same lesion pre- and on-treatment.

Basic information about the study treatments is provided in Table 2.

**Table 2: Details of Study Treatments/Intervention** 

Product Description and Dosage Form	Potency	Primary Packaging (Volume)/ Label Type	Secondary Packaging (Qty) /Label Type	Appearance	Storage Conditions (per label)
Nivolumab BMS-936558-01 Solution for Injection a	100 mg (10 mg/mL)	10 mL vial	5-10 vials per carton/ Open- label	Clear to opalescent colorless to pale yellow liquid. May contain particles	2 to 8°C. Protect form light and freezing
Ipilimumab Solution for Injection	200 mg (5 mg/mL)	40 mL vial	4 vials per carton/Open- label	Clear, colorless to pale yellow liquid. May contain particles	2 to 8°C. Protect from light and freezing.

a Nivolumab may be labeled as BMS-936558-01 Solution for Injection

If stored in a glass front refrigerator, vials should be stored in the carton. Recommended safety measures for preparation and handling of nivolumab and ipilimumab include laboratory coats and gloves. Please see Appendix 1 for further information.

# **Storage Conditions and Handling:**

Ipilimumab injection may be stored undiluted, 200 mg/vial (5 mg/mL), or following dilution to concentrations between 1 mg/mL and 4 mg/mL in 0.9% Sodium Chloride Injection (USP), or 5% Dextrose Injection (USP) in PVC, non-PVC/ or glass containers for up to 24 hours in the refrigerator (2°C to 8°C) or at room temperature/room light. For longer storage, ipilimumab should be kept refrigerated (2°C to 8°C) with protection from light.

Ipilimumab injection must not be frozen.

Partially used vials or empty vials of Ipilimumab Injection should be discarded at the site according to appropriate drug disposal procedures.

# 8.1 Details of Study Treatments/Intervention

#### 8.1.1 Ipilimumab

Mechanism of Action: CTLA-4 is a negative regulator of T-cell activity. Ipilimumab is a monoclonal antibody that binds to CTLA-4 and blocks the interaction of CTLA-4 with its ligands, CD80/CD86. Blockade of CTLA-4 augments T-cell activation and proliferation, including the activation and proliferation of tumor infiltrating T-effector cells. Inhibition of CTLA-4 can also reduce T-regulatory cell function, which may contribute to a general increase in T cell responsiveness, including the anti-tumor immune response.

Storage and formulation: Ipilimumab currently comes packaged in a concentrated form in either a 50 mg (5 mg/mL) or 200 mg (5 mg/mL) single use vial. This concentrated solution should be diluted with 0.9% Sodium Chloride or 5% Dextrose Injection to prepare a diluted

solution with a final concentration ranging from 1 mg/mL to 2 mg/mL. Ipilimumab must be stored at 2°-8°C. Vials should be protected from light and should not be frozen.

Pharmacokinetics: The pharmacokinetics of ipilimumab were studied in 785 patients with unresectable or metastatic melanoma who received doses of 0.3, 3, or 10 mg/kg once every three weeks for 4 doses. Peak concentration ( $C_{max}$ ), trough concentration ( $C_{min}$ ), and area under the plasma concentration versus time curve (AUC) of ipilimumab increased dose proportionally within the dose range examined. Upon repeated dosing every 3 weeks, the clearance (CL) of ipilimumab was found to be time-invariant, and systemic accumulation was 1.5-fold or less. Steady-state concentrations of ipilimumab were reached by the third dose; the mean  $C_{min}$  at steady-state was 19.4 mcg/mL following repeated doses of 3 mg/kg. The mean value for terminal half-life was 15.4 days and for CL was 16.8 mL/h.

Administration: Ipilimumab will be mixed, stored and administered as per commercial guidelines.

#### 8.1.2 Nivolumab

Mechanism of Action: Binding of the PD-1 ligands, PD-L1 and PD-L2, to the PD-1 receptor found on T-cells, inhibits T-cell proliferation and cytokine production. Upregulation of PD-1 ligands occur in some tumors and signaling through this pathway can contribute to inhibition of active T-cell immune surveillance of tumors. Nivolumab is a human immunoglobulin G4 monoclonal antibody that binds to the PD-1 receptor and blocks its interaction with PD-L1 and PD-L2, releasing the PD-1 pathway-mediated inhibition of the immune response, including the anti-tumor immune response.

Storage and formulation: Nivolumab currently comes packaged in a concentrated form in either a 40 mg (10 mg/mL) or 100 mg (10 mg/mL) single use vial. This concentrated solution should be diluted with 0.9% Sodium Chloride or 5% Dextrose Injection to prepare a diluted solution with a final concentration ranging from 1 mg/mL to 10 mg/mL. Nivolumab must be stored at 2°-8°C. Vials should be protected from light and should not be frozen.

Pharmacokinetics: The pharmacokinetics of nivolumab was studied in 909 patients over a dose range of 0.1 to 20 mg/kg administered as a single dose or as multiple doses every 2 or 3 weeks. The exposure to nivolumab increased dose proportionally over the dose range of 0.1 to 10 mg/kg administered every 2 weeks. The mean CL is 9.5 mL/h and mean elimination half-life is 25.7 days. Steady-concentrations of nivolumab were reached by 12 weeks when administered at 3 mg/kg every 2 weeks and systemic accumulation was approximately 3-fold.

Administration: Nivolumab will be mixed, stored and administered as per commercial guidelines.

#### 8.2 Toxicities / Side Effects

## 8.2.1 Ipilimumab

Likely Side Effects: Diarrhea, inflammation of the colon (colitis), increase in liver enzymes, fatigue, skin itchiness, skin rash, nausea, abdominal pain, decreased appetite, fever, vomiting, headache, constipation, adrenal gland abnormalities, and thyroid gland abnormalities.

Less Likely Side Effects: Chills, weakness, muscle pain, and redness of skin.

Rare Side Effects: Decrease or total loss of hormones of pituitary gland, allergic reactions, inflammation of the liver, inflammation of the pituitary gland, decreased red blood cells, loss of color (pigment) from areas of skin, decreased or blurry vision, or inflammation of the eye, numbness or tingling in your fingers or toes, inflammation or loss of the lining of the brain or spinal cord, inflammation of the kidneys, and joint pain.

# 8.2.2 Ipilimumab and Nivolumab

Likely Side Effects: Diarrhea, inflammation of the colon (colitis), increase in liver enzymes, fatigue, swelling of the extremities, flu-like feeling, pain, skin itchiness, skin rash or xerosis (increased dryness), vitiligo (loss of pigment or color in the skin), nausea, abdominal pain, decreased appetite, fever, vomiting, constipation, flatulence, dry mouth, weight loss, cough, shortness of breath, headache, peripheral neuropathy (numbness or tingling of the fingers or toes), dizziness, change in sensation of taste, joint pain or stiffness, dehydration, increased blood sugar, low sodium levels, infections, inflammation of the optic disc, low blood pressure, and difficulty sleeping.

Less Likely Side Effects: inflammation of the pancreas, decreased movement of the intestines, inflammation of the thyroid, lung inflammation (pneumonitis), shortness of breath, joint swelling, muscle soreness, weakness, stiffness, or spasm, adrenal gland abnormalities, inflammation of the heart or lining of the heart, acute kidney injury or failure, and increase in inflammatory blood proteins.

#### Rare Side Effects:

- Myasthenia gravis, a nerve disease that may cause weakness of the eye, face, breathing and swallowing muscles. One death in a patient who received the combination was considered due to myasthenia gravis and severe infection (sepsis)
- A syndrome associated with fever, WBC activation and abnormal function (including destruction of other blood cells by WBCs), low blood cell counts, rash, and enlargement of the spleen.

# 8.3 Treatment of Nivolumab or Ipilimumab Related Infusion Reactions

Since nivolumab and ipilimumab contain only human immunoglobulin protein sequences, it is unlikely to be immunogenic and induce infusion or hypersensitivity reactions. However, if such a reaction were to occur, it might manifest with fever, chills, rigors, headache, rash, pruritus, arthralgias, hypo- or hypertension, bronchospasm, or other symptoms.

All Grade 3 or 4 infusion reactions should be reported as an serious adverse event (SAE) if criteria are met. Infusion reactions should be graded according to National Cancer Institute (NCI) CTCAE 4.00 guidelines.

Treatment recommendations are provided below and may be modified based on local treatment standards and guidelines as appropriate:

For Grade 1 symptoms: infusion interruption not indicated; intervention not indicated

Remain at bedside and monitor participant until recovery from symptoms. The following prophylactic premedications are recommended for future infusions: diphenhydramine 50 mg (or equivalent) and/or acetaminophen 325 to 1000 mg at least 30 minutes before additional nivolumab administrations.

**For Grade 2 symptoms**: requires therapy or infusion interruption but responds promptly to symptomatic treatment (e.g., antihistamines, non-steroidal anti-inflammatory drugs, narcotics, corticosteroids, bronchodilators, intravenous [IV] fluids); prophylactic medications indicated for 24 hours.

Stop the nivolumab or ipilimumab infusion, begin an IV infusion of normal saline, and treat the participant with diphenhydramine 50 mg IV (or equivalent) and/or acetaminophen 325 to 1000 mg; remain at bedside and monitor participant until resolution of symptoms. Corticosteroid or bronchodilator therapy may also be administered as appropriate. If the infusion is interrupted, then restart the infusion at 50% of the original infusion rate when symptoms resolve; if no further complications ensue after 30 minutes, the rate may be increased to 100% of the original infusion rate. Monitor participant closely. If symptoms recur then no further nivolumab or ipilimumab will be administered at that visit. Administer diphenhydramine 50 mg IV, and remain at bedside and monitor the participant until resolution of symptoms. The amount of study drug infused must be recorded on the eCRF. The following prophylactic premedications are recommended for future infusions: diphenhydramine 50 mg (or equivalent) and/or acetaminophen 325 to 1000 mg should be administered at least 30 minutes before additional nivolumab or ipilimumab administrations. If necessary, corticosteroids (recommended dose: up to 25 mg of IV hydrocortisone or equivalent) may be used.

**For Grade 3 or Grade 4 symptoms:** Grade 3: prolonged (i.e., not rapidly responsive to symptomatic medication and/or brief interruption of infusion); recurrence of symptoms following initial improvement; hospitalization indicated for other clinical sequelae (e.g., renal impairment, pulmonary infiltrates). Grade 4: life threatening; pressor or ventilatory support indicated.

Immediately discontinue infusion of nivolumab or ipilimumab. Begin an IV infusion of normal saline, and treat the participant as follows. Recommend bronchodilators, epinephrine 0.2 to 1 mg of a 1:1,000 solution for subcutaneous administration or 0.1 to 0.25 mg of a 1:10,000 solution injected slowly for IV administration, and/or diphenhydramine 50 mg IV with methylprednisolone 100 mg IV (or equivalent), as needed. Participant should be monitored until the Investigator is comfortable that the symptoms will not recur. Nivolumab or ipilimumab will be permanently discontinued. Investigators should follow their institutional guidelines for the treatment of anaphylaxis. Remain at bedside and monitor participant until recovery from symptoms. In the case of late-occurring hypersensitivity symptoms (e.g., appearance of a localized or generalized pruritus within 1 week after treatment), symptomatic treatment may be given (e.g., oral antihistamine, or corticosteroids).

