# 7.3 Withdrawal, Removal, and Replacement of Participants

A participant may voluntarily withdraw or be withdrawn from the study at any time for reasons including, but not limited to, the following:

- Progression of disease: Either unequivocal symptomatic progression necessitating a change in therapy in the opinion of the treating physician or radiologic progression as defined by cross-sectional imaging utilizing RECIST 1.1 criteria.
- Treatment Cessation: Discontinuation criteria apply for all drug-related AEs attributed to nivolumab, ipilimumab or both. Treatment with all study drugs should be permanently discontinued for the following:
  - Any Grade 2 drug related uveitis or eye pain or blurred vision that does not respond to topical therapy and does not improve to Grade 1 severity within the re-treatment period OR requires systemic treatment
  - o Any Grade 3 non-skin, drug-related AE, with the following exceptions:
    - Grade 3 diarrhea lasting <7 days
    - Grade 3 drug-related laboratory abnormalities do not require treatment discontinuation except
      - ➤ Grade 3 drug-related thrombocytopenia >7 days or associated with bleeding requires discontinuation
      - Any drug-related liver function test abnormality that meets the following criteria requires discontinuation:
        - AST or ALT >8 x upper limit of normal (ULN)
        - Total Bilirubin >5x ULN
        - Concurrent AST or ALT and total bilirubin >2x ULN
  - Any Grade 4 drug-related AE or laboratory abnormality, except for the following events which do not require discontinuation.

- Grade 4 amylase or lipase abnormalities that are not associated with symptoms or clinical manifestations of pancreatitis.
- Isolated Grade 4 electrolyte imbalances/abnormalities that are not associated with clinical sequelae and are corrected with supplementation/appropriate management within 72 hours of their onset
- Any dosing interruption lasting >6 weeks with the following exceptions:
  - Dosing interruptions to allow for prolonged steroid tapers to manage drugrelated AEs are allowed.
  - Dosing interruptions >6 weeks that occur for non-drug related may be allowed if approved by the primary Investigator
- Any AE, laboratory abnormality or intercurrent illness which, in the judgment of the Investigator, presents a substantial clinical risk to the participant with continued drug dosing.
- Withdrawal of consent: Participant may withdraw consent at any time.
- Death

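### Protocol Section 8.3 handles symptoms that recur on restarting an infusion under Grade 2, but lists such recurrence as a Grade 3 criterion with permanent discontinuation, and does not link the two

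*Protocol*

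**What the plan says.** Protocol Section 8.3 requires infusion reactions to be graded by CTCAE 4.00. It then gives management steps by grade, introduced as recommendations that may be adapted to local standards.

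- **Grade 2, definition.** The reaction "requires therapy or infusion interruption but responds promptly to symptomatic treatment".
- **Grade 2, action.** "If the infusion is interrupted, then restart the infusion at 50% of the original infusion rate when symptoms resolve". Then: "If symptoms recur then no further nivolumab or ipilimumab will be administered at that visit". The block ends with advice that opens "The following prophylactic premedications are recommended for future infusions".
- **Grade 3, definition.** The criteria include "recurrence of symptoms following initial improvement; hospitalization indicated for other clinical sequelae".
- **Grade 3 or 4, action.** "Nivolumab or ipilimumab will be permanently discontinued".

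Protocol Section 7.3 has a general rule for drug-related adverse events attributed to either drug or to both: "Treatment with all study drugs should be permanently discontinued for the following". The list that follows includes Grade 3 drug-related events other than skin events. Its exceptions cover short-lived diarrhea and certain laboratory abnormalities, and infusion reactions are not among them.

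The Grade 1 text of Section 8.3 recommends premedication "at least 30 minutes before additional nivolumab administrations", without naming ipilimumab. The Grade 2 text names both drugs.

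**The concern.** A recurrence on restart is the specific situation that the Grade 2 text provides for, and it also fits a criterion that the next paragraph uses to define Grade 3. The actions attached to the two grades differ: one is worded for a single visit, the other is permanent. A nurse or investigator reading down the page reaches the Grade 2 instruction first and finds nothing there that leads on to the Grade 3 action.

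What is at stake is first the safety of the participant, who may be infused again at one site and permanently stopped at another. The data follow from that: the grade recorded, whether the Section 8.3 sentence on reporting Grade 3 or 4 reactions as serious comes into play, the number of doses received (SAP Section 5.5.1), and the summaries of events by severity and of events leading to discontinuation (SAP Section 5.5.2). These serve the secondary objective on safety and tolerability.

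**Working it through.** The plan gives no figure to reproduce, so the check consists of tracing one event through the text.

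1. A participant has a reaction that needs interruption and responds promptly. By the Section 8.3 definition it is Grade 2.
2. Symptoms resolve, and the infusion is restarted at half rate as the Grade 2 text directs.
3. Symptoms come back. Two parts of Section 8.3 now describe the event:

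| | Grade 2 text | Grade 3 text |
|---|---|---|
| How the event is described | Symptoms recur after restart | Symptoms recur after initial improvement |
| What happens to drug | None for the rest of that visit | Permanently discontinued |
| Later infusions | Foreseen, with premedication | None of the discontinued drug |
| Link to the other text | None | None |

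4. *Can the descriptions be separated?* One speaks of symptoms that resolve, the other of initial improvement. Resolution is a form of improvement, and the protocol draws no line between them.
5. *Does another section decide?* If the event is Grade 3, drug-related and not a skin event, Section 7.3 stops all study drugs. If it is left at Grade 2, that Grade 3 rule is not triggered, and Section 8.4.5 in general allows dosing to resume once a drug-related event has settled to Grade 1 or baseline. The action depends on the grade, and the Grade 2 text does not say that the grade changes.
6. *Which drugs stop in Arm A?* The Grade 3 or 4 action in Section 8.3 names the two drugs joined by "or"; Section 7.3 names all study drugs. The wording differs, although Section 7.3 expressly covers events attributed to one drug.

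**Doses that depend on the reading.** Section 8.4.1 plans 4 doses. If the event occurs at dose k, 4 − k later doses are at issue: 4 − 1 = 3 at the first dose, 4 − 2 = 2 at the second, 4 − 3 = 1 at the third and 4 − 4 = 0 at the fourth. The largest share is 3/4 = 75%.

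**Scale in the safety tables.** With 12 planned participants per arm, one participant is 1/12 = 8.3 percentage points. This is the weight of any single participant in any binary summary and does not estimate the effect of this conflict.

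**What does not move.** Everyone who receives at least one dose stays in the efficacy-evaluable population (Protocol Section 12.2; SAP Section 5.1.1), and SAP Section 5.4 includes participants regardless of adherence. Neither reading changes the denominator of the response rate.

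**The case against.** The best defence is that the text can be put in order. CTCAE 4.00 grading applies to all infusion reactions, and the protocol's own Grade 3 criteria include recurrence, so the event is Grade 3. Section 7.3 then governs, and it is not labelled a recommendation, whereas the Section 8.3 steps are. On this view the Grade 2 sentence is only same-day bedside management, and giving no more drug that day is compatible with never giving it again. The closing premedication advice serves every Grade 2 reaction, including those that never recur.

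Much of this stands. A reader might infer that the Grade 2 text orders treatment to continue after a recurrence. It does not: continuation is inferred mainly from the limitation to that visit. A reader might also infer that the documents give no guidance on grading, which the CTCAE requirement contradicts. But the reading order has to be assembled by the site, because no sentence states it. Freedom to adapt the steps locally does not reconcile them either.

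A second tempting inference is that an Arm A participant who reacts to nivolumab would be left on ipilimumab alone, in effect the Arm B regimen. The documents do not support that. Section 7.3 stops all study drugs for events attributed to either one, and Section 8.4.2, which concerns holds and not permanent stops, points the same way by holding both drugs in the combination arm. Section 8.3 also uses the two drug names joined by "or" for whichever infusion is running. What remains is a difference in wording that should be aligned.

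Finally, Section 8.3 calls such reactions unlikely, and the event needs a reaction, an interruption, a restart and a recurrence. That limits how often the conflict would matter, but the instruction still has to be clear when it is used.

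**Conclusion.** The conflict is real and the text needs correcting. Recurrence on restart is handled under Grade 2, yet it meets a Grade 3 criterion with a different action, and the Grade 2 text neither regrades it nor refers to that action. Following the page can lead either to re-exposure or to a permanent stop.

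For an affected participant, up to 3 of 4 doses are at issue. The number affected is unknown, because the documents give no event rate. If one assumed 0 to 2 such events per arm, the shift in a safety table would run from 0 to 2/12 = 16.7 points. That range is only the assumption restated and should not be read as the expected effect. It would also require that the participant had no other event of Grade 3 or higher (for the severity table) or no other adverse event leading to discontinuation (for that table).

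The link to Section 7.3 holds only for drug-related events that are not skin events. Seriousness is affected only where the reporting criteria are also met. A reader might infer a threat to the response result; the analysis population is the same under both readings, so the consequences lie in safety, exposure and the descriptive safety tables.

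The Grade 1 premedication wording, which names only the drug that Arm B does not receive, is a separate and minor inconsistency.

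**What to change.** Reconcile the Grade 2 and Grade 3 text of Protocol Section 8.3 with Section 7.3, so that symptoms recurring on restart have one grade and one action, stated or cross-referenced at the point in the Grade 2 text where recurrence is mentioned. Align the wording of Sections 8.3 and 7.3 on which drugs a permanent stop covers in Arm A. As a minor item, reconcile the drugs named in the Grade 1 premedication sentence with the Grade 2 wording. The sponsor's clinical team decides which action applies, and this review takes no position on it.

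The cost is a few sentences in a formal amendment, which Section 13.8.1 requires for any change. No new procedure or data item is needed, and the SAP tables can stay as they are.
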